4.4 Tolerability and Ease-of-Use Variables

Investigational eye drop tolerability (eye drop sensation upon instillation), as reported by each subject, will be captured in subject diaries as defined in Appendix B.

Ease-of-use of the bottle will be also assessed by each subject and captured in the diary according to Appendix B.

4.5 Appropriateness of Variables

In this study, all assessments and variables to assess the performance and safety of CBL-102 Eye Drops are considered standard practice in the field of ophthalmology for diagnosis and management of subjects with dry eye²⁹⁻³³.

Ocular surface staining has been chosen as the primary endpoint as it assesses the protective properties of the tear substitutes on the cornea and conjunctiva in dry eye¹³. The Oxford Scheme provides a logarithmic scale for grading of the ocular surface staining and is considered valuable for distinguishing changes²⁹⁻³⁰.

4.6 Risk Assessment

In rare cases Aqualarm[®] U.P., CBL-102 Eye Drops, and Vismed[®] Multi can cause hypersensitive reactions such as local allergic reactions. Refer to the patient information leaflet for approved product information for Aqualarm[®] U.P., CBL-102 Eye Drops, and Vismed[®] Multi which will be provided with the ICF.

The subjects will be informed of any known risks in the ICF. If additional risks are identified, the Sponsor will notify the Investigators.

5.0 STUDY METHODS

5.1 Study Visits

Refer to Appendix A for a schedule of visits and parameters and Appendix B for methods of clinical evaluation.

Subjects will be asked not to instill their tear substitute (if possible) within the hour before each visit.

Following identification of a potential subject, the Investigator (or designee) will explain the purpose of the study, procedures, risks/benefits, and subject responsibilities to the potential subject. The subject's willingness and ability to meet the follow-up requirements of the study will be determined. If the subject chooses to participate in the investigation, written informed consent will be obtained. The subject and the person obtaining written consent will sign and date the EC-approved ICF, at which point the subject is considered part of the study population. The original signed document will be retained in the subject records, and a copy will be provided to the subject. In addition, the applicable privacy regulation requirements must be met. An ICF must be signed prior to the start of any study-related procedures/assessments.

5.1.1 Visit 1 (Screening, Day -14 (up to -16 days))

- After obtaining written informed consent, prospective subjects will be screened to determine whether they meet the preliminary eligibility criteria for the study as follows:
 - Collect demographic information
 - Collect current and relevant medical and ophthalmic history
 - Identify concomitant medications used
 - Perform a urine pregnancy test, as applicable
- If the subject meets the preliminary eligibility criteria, perform the following:
 - Symptoms assessment
 - VA measurement
 - Biomicroscopy assessments
- Biomicroscopy will be assessed for each of the following:

 - Lids
 - Ocular discharge
 - Conjunctiva (chemosis and hyperemia)
 - Cornea (erosion, edema, and infiltrates)
- TFBUT measurement
- Fluorescein staining

If the subject meets the dry eye eligibility criteria on Visit 1, complete the following:

Study #CBL-2017-01- Protocol

- Dispense a subject diary (Diary A) to record run-in ART instillation frequency per day
- Dispense run-in ART
- Remind the subject that both eyes should be treated as needed (not by habit) up to 6 times per day with run-in ART to relieve dry eye symptoms
- Instruct subject to bring run-in ART and subject diary (Diary A) to Visit 2 and that dry eye eligibility testing will be completed at Visit 2

5.1.2 Visit 2 (Baseline/Randomization, Day 0)

- Collect AEs and changes in concomitant medications
- Collect subject diary (Diary A) and review for compliance
- Collect run-in ART
- Determine if the subject meets Visit 2 dry eye eligibility criteria by performing the following:
 - Symptoms assessment
 - VA measurement
 - Biomicroscopy
 - TFBUT measurement
 - Fluorescein staining
- If the subject meets the dry eye eligibility criteria on Visit 2, proceed as follows:
 - Perform the Schirmer test
 - Have the OSD-QoL® questionnaire completed by the subject
 - Dispense the investigational eye drops from the next sequential kit number to the subject
 - Instruct the subject to instill 1 drop of investigational eye drops in each eye 3 to 6 times per day
 - Provide new subject diary (Diary B) to the subject to record investigational eye drop instillation frequency, investigational eye drop tolerability upon instillation and ease-of-use of the bottle
 - Instruct the subject to bring their diary (Diary B) with them to Visit 4
 - Instruct the subject to put their used and remaining unused bottles in the container (kit box provided at Visit 2) for retrieval at the end of the study

5.1.3 Visit 3 (Day 7 ± 1 day, Safety/compliance Telephone Assessment)

- Assess treatment compliance
- Collect any adverse event since the previous visit and changes in concomitant medication

Study #CBL-2017-01- Protocol

- Determine in the subject should come to the site for a visit or not

If the subject comes to the site, proceed as follows:

- Confirm AEs and changes in concomitant medications
- Perform the following assessments:
 - VA measurement
 - Biomicroscopy
- Study personnel will review the subject diary (Diary B) for compliance and then return it to the patient

For both the telephone assessment and the visit at site:

- Remind the subject to instill 1 drop of investigational eye drops in each eye 3 to 6 times per day
- Remind the subject to record investigational eye drop instillation frequency, investigational eye drop tolerability upon instillation and ease-of-use of the bottle in diary
- Instruct the subject to bring their subject diary with them to Visit 4
- Remind the subject to continue to put their used and remaining unused bottles in the container (kit box provided at Visit 2) for retrieval at the end of the study

5.1.4 Visit 4 (Day 28 ± 3 days)

- Collect AEs and changes in concomitant medications
- Perform the following assessments:
 - Symptoms
 - VA
 - Biomicroscopy
 - TFBUT measurement
 - Fluorescein staining
 - Schirmer test
- Collect subject diary (Diary B) and review for compliance
- Dispense new investigational eye drops kit
- Remind the subject to instill 1 drop of investigational eye drop in each eye 3 to 6 times per day
- Provide new subject diary (Diary C) to the subject

Study #CBL-2017-01- Protocol

- Remind the subject to record in diary investigational eye drop instillation frequency, investigational eye drop tolerability upon instillation and ease-of-use of the bottle
- Instruct the subject to bring their subject diary with them to Visit 5
- Instruct the subject to put their used and remaining unused bottles in the box (kit box provided at Visit 4) and to bring the two kit boxes in a sealed container at Visit 5

5.1.5 Visit 5 (Study Exit, Day 90 ± 10 days)

- Collect AEs and changes in concomitant medications
- Perform the following assessments:
 - Symptoms
 - OSD-QoL® questionnaire
 - VA
 - Biomicroscopy
 - TFBUT measurement
 - Fluorescein staining
- Collect subject diary (Diary C) and review for compliance
- Collect the sealed container of investigational eye drops for accountability
- Exit the subject from the study

NOTE: *All investigational eye drops and subject diaries should be returned at this visit.*

5.1.6 Unscheduled Visits

Additional visits may be scheduled, as necessary, to ensure the safety and well-being of subjects. All additional exams should be fully documented in the source documents and on Unscheduled Visit eCRFs, as appropriate. Visits intended to fulfill scheduled visit requirements that fall outside the designated scheduled visit range, are not Unscheduled Visits. In these cases, the visit data will be collected and transcribed to the appropriate scheduled visit eCRF.

If a subject is seen for multiple visits during a given visit time frame, the data from the visit that is intended to meet the protocol requirements for the scheduled visit should be captured on the visit eCRF. Where such a determination cannot be made, the first visit within the scheduled visit interval will be used for completion of the protocol required scheduled visit eCRF. Data from any additional visits within a scheduled visit interval will be captured on an Unscheduled Visit eCRF.

5.1.7 Missed Visits

If a subject misses any scheduled follow-up visit and cannot be seen prior to the start of the visit range for the next scheduled follow-up visit, the visit is considered missed.

5.2 Post-study Follow-up

If a subject requires further follow-up on AEs upon discontinuation or completion of the study, the Investigator should schedule post-study follow-up visits, as necessary. Refer to Sections 6.0 for follow-up of AEs following study exit.

5.3 Study Completion

The Sponsor Representative will contact the EC to inform them that the study is completed.

5.3.1 Early Study Termination

If during the study it becomes evident to the Sponsor that the study should be stopped prematurely, then the study will be terminated and appropriate notification will be given to the Investigator(s), EC, and Local Health Authority, as applicable. The Sponsor will instruct the Investigators to stop dispensing study materials/treatment and to arrange for study closeout at each site.

5.4 Concomitant Medications/Therapy

Administration of all medications used up to 30 days prior (immunosuppressants up to 90 days prior) to study entry (date ICF signed) through study exit must be reported in the source and appropriate section of the Concomitant Medications eCRF.

5.4.1 Permitted Therapy

- With the exception of the disallowed medications in Section 5.4.2, any medications that, in the Investigator's judgment, will not interfere with the study parameters are allowed to be used concurrently.
- Concomitant systemic medication that could affect dry eye (Section 5.4.2) but whose condition is stable for at least 1 month prior to Visit 1 will be continued, provided that it is not intended to alter the type, dose, and regimen of the medication during the trial.

5.4.2 Disallowed Therapy

No other ocular medications (with the exception of run-in ART) may be used during the study. A disallowed medication may be administered in an emergency if the subject's safety is in jeopardy. Disallowed medications include the following:

- Ocular therapy (either eye) with any ophthalmic solutions, including tear substitutes except the run-in ART provided.
- Systemic medication prescribed during the study and that could affect dry eye: antiparkinsonians, antidepressants, anxiolytics, neuroleptics, beta-blockers, clonidine, amiodarone, thiazide diuretics, anticholinergics, antihistamines, tetracyclines, anti-androgens, hormone replacement therapy, oral retinoids, anti-inflammatories, antineoplastic agents and immunomodulators^{1,31}.
- Any medication that the Investigator feels may interfere with study parameters.

5.5 Treatment Compliance

To document treatment compliance, subjects will be provided with diaries and instructed to record the frequency of instillations of investigational eye drops and the frequency of run-in ART instillations. Subjects will also be instructed to bring the diary to each visit.

Any subject who does not follow instructions to a degree that, in the Sponsor or Investigator's opinion, jeopardizes the subject's well-being or the validity of the study, must be discontinued.

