2.2.3 Subject Discontinuation

A subject MAY be discontinued (at the discretion of the Investigator, the Sponsor, and/or the EC) prior to the final visit for several reasons, including, but not limited to:

- A serious adverse event (SAE) occurring during the course of the study, which precludes continued treatment or follow-up
- The subject not following required study procedures
- If a subject exhibits intolerable AEs (related or not related to the investigational medical device), or if a subject fails to show improvement or the clinical status worsens, the treating Investigator may opt to withdraw the subject from the study and implement necessary intervention.

A subject MUST be discontinued prior to the final visit for any of the following reasons:

- Voluntary withdrawal
- Death
- Investigator decision that it is not in the best medical interest of the subject to continue participation in the investigation. In case a subject administers more than 8 instillations per day for both eyes on a regularly continued basis (approximately 70 %) as assessed on Visit 4, the subject will be discontinued from the study and the investigator will prescribe an appropriate treatment.

Prior to discontinuing a subject, every effort should be made to contact the subject, schedule a final visit, obtain as much follow-up data as possible, and to retrieve all investigational materials. Adverse events will be followed as described in Section 6.5 . Subject withdrawals will be documented clearly on the source document and applicable electronic case report form (eCRF). The assessments scheduled for Visit 5 should be performed at this early termination visit.

Notification of subject discontinuation will be made to the Sponsor Representative and will be clearly documented on the applicable eCRF. Any subject discontinued from the study will not be replaced.

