5.6 Protocol Deviations

The date of and reason for protocol deviations will be documented in all cases.

Protocol assessments will continue until the end of the study, unless the protocol deviations put the subject at risk or the subject's condition requires that he/she be discontinued from the study.

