7.6.6 Protocol Deviations

The number of subjects within each type of protocol deviations will be presented using listings and discrete summary statistics as appropriate. Protocol deviations will include, but are not limited to:

- Non-compliance with any scheduled study visit
- Non-compliance with investigational medical device treatment
- Disallowed concomitant medications
- Non-compliance with study inclusion or exclusion criteria
- Non-compliance with study assessment procedures

Deviations with a significant impact on the primary endpoint will be assessed as major deviations.

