7.6.9 Missing Data

For subjects who discontinue the study early, analyses of change from baseline to endpoint for continuous variables will be based on the last non-missing post-baseline data (last observation carried forward data imputation methodology).

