## 5 POPULATIONS DEFINITIONS

Populations	
Population	Definition
Screened population	All screened patients
Intent-to-Treat Population (ITT)	All subjects who were randomized, who received at least 1 investigational eye drop instillation and have a baseline and at least 1 post-baseline assessment.  The ITT population will be used to analyze all performance endpoints.
Per Protocol Population (PP)	All subjects from the ITT population who remained in the study through Visit 4 (Day 28) and who did not have any major protocol deviations*.  The PP population will be used for the primary performance analysis and for secondary performance endpoints.
Safety Population	All subjects who received at least 1 dose of investigational eye drops

Protocol deviations will include:

Code	Category
1	Non-compliance with consent procedure
2	Non-compliance with inclusion/Exclusion criteria
3	Non-compliance with study eye qualification
4	Non-compliance with visit schedule
5	Non-compliance with assessment procedure
6	Non-compliance with study product randomisation
7	Non-compliance with study product administration
8	Non-compliance with concomitant medication
9	Other* (to be defined if needed during the masked review)

Major protocol deviations (deviations with a significant impact on the primary endpoint) will be confirmed during the masked review.

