## 7.6 Secondary performance endpoint analyses

All secondary performance endpoint analyses will be performed on the ITT and PP populations. Results of statistical tests will be two-sided and given for information purpose only.

The secondary performance variables will be described by treatment group at each visit on raw values and on the changes / baseline D0.

The treatment groups will be compared at each post-baseline time using the same covariance model used to analyze the primary endpoint. The interaction Treatment x Baseline will be tested and removed from the model if not significant. If significant, the interaction will be kept in the model (a graphical representation of the interaction will be displayed) and the Treatment effect will be approximated by using the global average of observed D0 values (Note that in case of interaction, the Treatment effect cannot be properly interpreted). In addition, the distribution of the residuals of the analysis of variance will be tested: if the normality is not verified (Shapiro-Wilk test at the 1% threshold), the analysis will be performed on the ranks of the data (if analyses on ranks and on raw values lead to the same conclusions, only analysis on raw values will be given).

Depending on the distribution of the data (multinomial data such as global assessment of dry symptoms evaluations), a sensitivity analysis will be performed to compare both groups using a generalized linear model for multinomial data (SAS® Glimmix Procedure) with the value at baseline as covariate.

For the Ocular surface fluorescein staining test, the % of patients with a total score at 0 at D28 and D90 will be given with its 95% confidence interval.

Graphical representations by bar charts will be provided for dry eye symptoms and OSD-QoL dimension scores.

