## 7.10 Compliance and exposure to treatment

Results of statistical tests will be two-sided and given for information purpose only.

Listings of subjects compliance masked data will be provided for the masked review meeting to determine treatment compliance deviations.

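### Section 5.5 mandates study exit on an opinion about study validity, against 5.6 and 2.2.3; the exit costs follow-up data and, before Visit 4, bypasses masked review of PP membership (minor)

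*Protocol*

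**What the plan says.** Three protocol sections govern a subject who does not use the drops as instructed.

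- **Section 5.5** requires discontinuation when the sponsor or investigator thinks the non-adherence threatens either the subject or the study: such a subject "jeopardizes the subject's well-being or the validity of the study, must be discontinued". No threshold is given.
- **Section 5.6** says "Protocol assessments will continue until the end of the study, unless the protocol deviations put the subject at risk"; the only other exception is that the subject's own condition requires exit. Section 7.6.6 lists "Non-compliance with investigational medical device treatment" among the deviations, so 5.6 covers the same subject.
- **Section 2.2.3** puts "The subject not following required study procedures" among the grounds on which a subject MAY be discontinued. Its MUST list has voluntary withdrawal, death and the investigator's judgement of medical interest. Study validity is not on it.

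On the analysis side, the PP set takes ITT subjects who stayed in the study through Visit 4 and had no major deviation (Protocol 7.5, SAP 5). SAP 5 adds: "Major protocol deviations (deviations with a significant impact on the primary endpoint) will be confirmed during the masked review". Under SAP 7.10, listings of masked compliance data "will be provided for the masked review meeting to determine treatment compliance deviations". PP is primary for the Day 28 endpoint and ITT is supportive; secondary endpoints are analysed in both. For subjects who leave early, change from baseline in continuous variables "will be based on the last non-missing post-baseline data" (Protocol 7.6.9, repeated in SAP 7.12).

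**The concern.** For a subject who is non-adherent but not at risk, one section requires exit, one requires assessments to continue and one leaves the choice open. Two sites could treat the same subject differently and each could point to the protocol.

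The exit happens after randomization and rests on opinion. It stops data that would otherwise be observed at visits already scheduled. If it happens before Visit 4, it also settles PP membership outside the masked review to which the SAP gives that decision. At stake are the supportive ITT result at Day 28, the Day 90 results in both sets, and part of the 90-day safety record, which belongs to the primary objectives (1.0).

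**Working it through.** **1. Does discontinuation mean leaving the study?** Yes. Section 2.2.3 describes it as happening before the final visit, with an early-termination visit and return of materials. Section 5.6 also speaks of discontinuation from the study. Neither document defines a status of stopping the product while staying under observation.

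**2. The rules side by side, for a non-adherent subject not at risk**

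| Section | Instruction | Is study validity a ground for exit? |
|---|---|---|
| 5.5 | Must exit, if the sponsor or investigator so judges | Yes |
| 5.6 | Assessments continue to the end | No |
| 2.2.3 | May exit | Not named |

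**3. What an exit changes, by timing**

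- *Before Visit 4.* The subject fails the requirement to remain through Visit 4 and leaves PP automatically, whether or not masked review would have called the deviation major. Staining is scheduled at Visits 1, 2, 4 and 5 only (Appendix A), so the early-termination exam is the one value available to carry forward to Day 28 in ITT. The scheduled prompt for such an exit is the Day 7 call. From there to Visit 4 is 28 - 7 = 21 days (25 - 8 = 17 to 31 - 6 = 25 over the windows). An unscheduled visit could prompt an earlier exit.
- *At or after Visit 4.* Diary B is reviewed at Visit 4 (5.1.4), which makes that visit a natural trigger. The Day 28 value is observed. The Day 90 values become carried-forward values, in ITT and also in PP for subjects who stay in that set.

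**4. Safety follow-up lost after an exit at Visit 4**

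- Routine collection of new adverse events ends at study exit (4.3, 6.8). Days lost before Day 90: 90 - 28 = 62. Range over the windows: 80 - 31 = 49 to 100 - 25 = 75.
- For 30 days after exit, ongoing non-serious events are still followed (6.8). All SAEs are reported to 30 days after the last dose (6.9), taken here as the exit day. What remains is 62 - 30 = 32 days (49 - 30 = 19 to 75 - 30 = 45), in which only related SAEs are reported.
- If the product stops at exit, these are off-product days, so little evidence on exposure to CBL-102 is lost.

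**5. How many subjects**

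The plan's sample size reproduces. Inputs from 7.3: one-sided alpha 0.025, power 90%, margin 2, SD 2.5. A true difference of 0 is assumed, since none is stated.

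- n per group = 2 x (1.960 + 1.282)^2 x 2.5^2 / 2^2 = 32.8, rounded up to 33.
- 33 / (1 - 0.20) = 41.25, rounded up to 42 per group, or 84 in total.

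The planned violation rate is 10% x 84 = 8.4 subjects, from all causes. The share who would be exited under 5.5 is not given, so a range is assumed:

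| Share of violators exited | Additional exits | Total early exits, including the planned 10% dropout |
|---|---|---|
| 0% | 0 | 8.4 (10%) |
| 25% | 2.1 | 10.5 (12.5%) |
| 50% | 4.2 | 12.6 (15%) |
| 100% | 8.4 | 16.8 (20%) |

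PP planning power stays at about 90%, because violators are already netted out of the 33 per group. No shift in the ITT estimate is computed; the documents give no inputs for one.

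**The case against.** The best defence is that 5.5 is a specific rule that overrides the general rule in 5.6, and that ending follow-up of a seriously non-adherent subject is a legitimate choice. Keeping such subjects may pull the arms together, which in a non-inferiority trial favours the conclusion sought. The plan also softens the loss. Section 2.2.3 asks for every effort to hold a final visit with the Visit 5 assessments, which include staining. The SAP lists non-compliance as a reason for premature end of study (6.8) and reports discontinuations by group (7.3). Investigators and sponsor staff involved in conduct are masked (3.8), which limits bias in who is exited.

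Most of this stands, and it keeps the grade low. It does not remove the point: a specific-over-general reading still leaves an exit by opinion after randomization, and before Visit 4 that exit takes the PP decision away from masked review. Opinion would also still govern the well-being ground, so site differences would shrink but not vanish.

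A reader might go further and infer that PP exclusion already does everything the exit does. The documents do not support that. Major deviations are defined by impact on the primary endpoint, which is at Day 28, so non-adherence arising after Visit 4 need not remove anyone from PP. The exit does not solve that problem either, since it puts an earlier value in place of the Day 90 one. A reader might also infer that only ITT and safety data are lost; step 3 shows that PP loses subjects or Day 90 values too.

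**Conclusion.** The inconsistency is real and minor. It affects an unknown number of subjects: from none to about 8 of 84 if up to all planned violators were exited, which is an assumption. Per subject, an exit before Visit 4 costs PP membership and an observed Day 28 ITT value. An exit at Visit 4 costs the observed Day 90 values in both sets and 62 days of routine collection of new non-serious events.

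The consequences are bounded. The Day 28 ITT analysis is supportive. For the Day 90 performance endpoints, SAP 7.6 states: "Results of statistical tests will be two-sided and given for information purpose only". It would be wrong to infer that the primary non-inferiority conclusion or its power is threatened: the sample size already allows for violators, and a subject exited early for serious non-adherence might well have been excluded at masked review anyway. The conclusion assumes that discontinuation in 5.5 means study exit, as in 2.2.3, and that the last dose coincides with exit.

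**What to change.** - **5.5:** remove study validity as a ground for study exit; keep subject well-being.
- **2.2.3 and 5.6:** align them so that a non-adherent subject who is not at risk is still asked to attend Visits 4 and 5 on schedule unless consent is withdrawn.
- **PP membership:** leave it to the masked review, as the SAP already plans.
- **No change** to the 2.2.3 rule on more than 8 instillations a day, which is a medical-interest rule consistent with 5.6, or to SAP 7.12.

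The cost is one wording amendment to three sections, with ethics committee approval before use (8.6). The visits are already scheduled, and neither the SAP, the eCRF nor the sample size changes. The trade-off is that some ITT values, and some Day 90 PP values, will come from poorly adherent or off-product subjects and may bring the arms closer together. PP should therefore remain the primary set.
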